11. DATA AND SPECIMEN MANAGEMENT

11.1 Data analysis plan

Aim 1 Analysis Plan. The proposed trial uses a cluster-randomized design where the practice location is the unit of randomization. We will randomize 12 locations to two arms (usual care, EMC2) resulting in 6 per arm. Locations will be matched by total number of patients eligible for the study as well as proportion of Spanish speaking patients, with one location from each pair randomized to each arm. We will accrue ~100 patients per location, on average, and conservatively anticipate ≥80% retention at 3-month follow-up. These estimates result in 1200 participants recruited with an anticipated 960 patients (480 per arm, 80 per location) available for primary data analysis.

Medication knowledge associated with high-risk medications is the first primary outcome of interest for Aim 1 (H1), and will be analyzed as a score ranging from 0-100 reflecting the percent of items correct for each medication. Medication use outcomes (proper use, adherence) and detection of ADEs are relevant to the other hypotheses of interest for Aim 1 (H2, H3). Associations between the outcomes and potential confounders at the patient (socio-demographic characteristics, comorbidities, # and type of medications taken, previous history with side effects, literacy, and primary language) and medication (drug type, route of administration) levels will be examined. We intend to use generalized linear mixed models (GLMM) to analyze the data, which can handle data that is missing at random (MAR). Additionally, we will examine rates of missing data, and determine if there are any discernible patterns using GLMMs with a logit link function to predict the presence of missing data. Should we find significant predictors, we will use multiple impute methods and present results as secondary analyses.

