To account for the correlated nature of the data from participants at the same practice and multiple observations per patient, we will use GLMMs for analyses of all data, specifying identity link for continuous and the logit link for binary outcomes using PROC GLIMMIX in SAS (v.9.4). Treatment assignment by time will be the independent variable of primary interest and modeled as a fixed effect and practice location as a random effect, with additional subject statement to model correlations within patient. We will also include fixed effects for any potential confounding covariates noted in the descriptive studies. For all GLMM analyses we will report point estimates and 95% confidence

STU#: 00201638

intervals, and the extent to which random effects suggest correlation of outcomes within practice location. Additionally, we will estimate the ICCs for all outcomes to be used in future studies.

Aim 2 Analysis Plan: We will repeat all GLMM analyses described in Aim 1, but with the inclusion of a fixed effect for participants' literacy defined as limited (inadequate or marginal literacy) vs. adequate. We will formally test for differences in intervention effects according to literacy by including a literacy-intervention interaction term. Statistically significant interaction terms ($p < 0.05$) will indicate that the disparities in understanding between the intervention and usual care group vary by literacy level. Similar analyses will be used to test for interactions of intervention effects by age and English proficiency (using Census criteria of 'very well' vs. 'less than very well').

Aim 3 Analysis Plan: Following completion of enrollment, we will determine the extent to which the intervention was implemented as planned in the intervention arm. We will ask patients in the intervention arm if they were counseled, and whether they received the Med Guide Summaries and the post-visit IVR call. Bivariate analyses will be performed to compare relevant outcomes for H4-H7 between arms using t-tests, Wilcoxon Rank-Sum, or χ^2 tests, as appropriate. Aim 3 findings will also directly inform follow-up qualitative investigations in Aim 4.

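### Covariates for the Aim 1 models are chosen from outcome associations with no stated rule, and neither patient language nor the clinic matching is a required model term

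*Combined protocol and SAP*

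**What the plan says.** The analysis text is all in section 11.1 of the combined protocol and SAP.

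- **Matching.** "Locations will be matched by total number of patients eligible for the study as well as proportion of Spanish speaking patients". Allocation is then split within each matched set: "with one location from each pair randomized to each arm".
- **Candidate covariates.** The plan looks first at "Associations between the outcomes and potential confounders at the patient" level and at medication level. The list runs from socio-demographics and comorbidities to "previous history with side effects, literacy, and primary language) and medication (drug type, route of administration) levels will be examined". No clinic-level variable is on it.
- **Covariates in the model.** The model then takes in "fixed effects for any potential confounding covariates noted in the descriptive studies". No final list, threshold or rule is given. The descriptive work is not defined, and the only step that fits the description is the look at outcome associations.
- **Required terms.** Treatment by time is "modeled as a fixed effect and practice location as a random effect, with additional subject statement to model correlations within patient". The matched pair, the Spanish-speaking share and the count of eligible patients are not among the required terms.
- **Literacy.** Aim 2 adds a literacy effect to the Aim 1 models, so it is not fixed in Aim 1.
- **Clinic count.** "We will randomize 12 locations to two arms (usual care, EMC2) resulting in 6 per arm", and section 29 also refers to 12 locations. Sections 3.1, 3.2 and 19.1 describe seven clinics, and section 3.2 names three as the intervention clinics.

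**The concern.** The covariate set for the main comparison is settled only after outcome data have been examined, and by no stated criterion. Two analysts following the text could fit different models. Because the screen is run against the outcomes, each Aim 1 outcome could also end up with its own set. For proper use, a yes/no outcome with a logit link, this goes beyond precision: odds ratios are not collapsible, so a different covariate set estimates a different quantity even under perfect balance.

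The design treats language mix as important enough to match on, and section 2.1 links limited English proficiency to more misuse and non-adherence, and limited literacy to poorer understanding. Yet patient language, the patient-level counterpart of a matching factor, is only one candidate among many, and clinic volume and the pair are not even candidates. If seven clinics were randomised three to four, complete pairs cannot exist, so balance on language is less secure and adjustment matters more.

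**Working it through.** **1. The plan's own figure.** Inputs from section 11.2: SD 28.4, 480 analysed per arm, ICC 0.001, 80 analysed (100 enrolled) per clinic, 80% power, 5% error (two-sided assumed).

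- Design effect = 1 + (80 − 1) × 0.001 = 1.079.
- Standard error = 28.4 × √(2 × 1.079 / 480) = 1.90 points.
- Detectable difference = (1.960 + 0.842) × 1.90 = 5.33. With 100 per clinic, the design effect is 1.099 and the difference 5.38.

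The stated 5.5 is slightly conservative. It does not depend on the covariate rule.

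**2. How far unadjusted language mix could move a 3-month contrast.** The documents give neither the spread of Spanish share between clinics nor a language effect, so both are assumed. Take three versus four clinics, equal weight per clinic and no matching:

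added SD = (SD of share) × √(1/3 + 1/4) × (language effect), where √(1/3 + 1/4) = 0.764.

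| SD of Spanish share | SD of arm difference in share | 5-point effect | 10-point effect |
|---|---|---|---|
| 10 points | 0.076 | 0.38 | 0.76 |
| 20 points | 0.153 | 0.76 | 1.53 |
| 30 points | 0.229 | 1.15 | 2.29 |

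The range is 0.4 to 2.3 points against a planned standard error of 1.9. In ICC terms, the middle row alone implies 0.20² × 5² = 1 to 0.20² × 10² = 4 points² of between-clinic variance. Divided by 28.4² = 806.6, that is 0.0012 to 0.005, above the planned 0.001.

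**3. Would a screen catch language?** Assume a p < 0.05 screen, 960 patients and 15% to 50% Spanish speakers. The standard error of the language difference is 28.4 / √(960 × p × (1 − p)), which is 2.57 at 15% and 1.83 at 50%. A 5-point effect is then retained in about 50% to 78% of trials, and a 10-point effect in 97% or more.

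**4. Behaviour of the test.** This was a simulation with no treatment effect: t-tests on clinic means rather than the planned mixed model, 1,500 runs per setting. It used 12 pair-matched clinics of 80 or 7 unmatched clinics of 137, ICC 0.001 or 0.01, language effects of 0, −4, −8 and −12 points, and ten other candidates. All language inputs are assumptions.

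- *Twelve matched clinics, effect −12:* ignoring language and pairing lowers type I error to 1.5% to 2.3%. Adjusting for language restores 4.8% to 5.1%.
- *Seven clinics, ICC 0.001:* adjusting for language cuts the SD of the estimate from 2.47 to 1.97 (effect −8) or from 2.89 to 1.96 (effect −12). The removed component at −8 is √(2.47² − 1.97²) = 1.49 points. That corresponds to a share SD of 1.49 / (8 × 0.764) = 0.24, inside the range in step 2.
- *Mechanical p < 0.05 screen:* type I error is 4.2% to 6.1%, with Monte Carlo error of about 0.6 points. At a −4 point effect, language is kept in 53% to 55% of trials.
- *Smallest p-value among six covariate sets:* about 6% to 8% with 12 clinics and 7% to 11% with seven.

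**The case against.** Much can be said for the plan.

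- **The pool is named in advance and contains primary language and literacy.** A reader might infer that language is left out of the model. It is not; it is optional. Step 3 also shows that the largest shifts in step 2 are those a screen would nearly always pick up. This stands, and leaves moderate effects, retained about half to three-quarters of the time, as the main exposure.
- **The added SD is variation across randomisations, not bias.** The random clinic effect is meant to carry between-clinic variation, language mix included, into the standard error. This stands: a reader might infer that the treatment effect is biased, and the documents do not support that.
- **Type I error.** A reader might infer that selecting covariates by outcome association inflates it. A mechanical screen did not do so materially, and the 7% to 11% figure needs a free choice of the most favourable model, which the documents do not describe. They do not rule it out either, because no rule is given.
- **Balance need not be purely random.** Seven clinics could form three pairs with one left over, and step 2 gives no credit for that. This stands. The conflict between 12 and seven clinics is also a separate matter to reconcile.
- **Treatment by time is the term of primary interest.** If the interaction is the estimate, a language offset constant over time cancels. This stands in part. Section 11.2 sizes the trial on the 3-month comparison, and the baseline interview follows the in-clinic components, so change from baseline is not clearly the intended contrast.

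**Conclusion.** The concern holds as a weakness of specification that should be corrected. The plan describes a method, choosing covariates from associations with the outcome, without the rule that would make it reproducible, and the model does not reflect the matching. Under either clinic count there is a cost: a test that is too conservative if 12 matched clinics are analysed without language or pairs, or a less precise estimate if seven unmatched clinics are. The added SD is comparable with the planned standard error only at the upper end of the assumed ranges and only if language stays unadjusted. The documents do not show that the reported effect would be wrong; they leave it open to vary with a decision taken after outcomes are seen.

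**What to change.** Keep the model structure of section 11.1: treatment, time, treatment by time, random clinic and within-patient correlation. Before outcomes are examined by arm, fix one covariate set for all Aim 1 outcomes: patient primary language, age and literacy category, stating which literacy grouping is used. Drop selection by observed association with the outcome. Make any other adjustment a labelled sensitivity analysis, including drug type, which the alert described in section 9.2 could affect because it fires while the order is being placed.

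State how the matching is handled, once the clinic count is reconciled:

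- If pair-matched randomisation was carried out, include the pair. With 12 clinics this leaves 5 rather than 10 clinic-level degrees of freedom. At the step 1 standard error, the detectable difference on a noncentral t moves from 5.92 to 6.69 points, before any credit for variance that pairing removes.
- If seven clinics were randomised, say that patient-level language is used in place of clinic-level terms, to save degrees of freedom, and that clinic volume is deliberately omitted.

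The cost is wording. Language and age come from the screening data and literacy from the baseline interview. What is given up is the freedom to add covariates to the primary model later.

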19. SETTING

19.1 Research sites.

Sites from which we will recruit participants (via phone) include clinics associated with The Alliance, an EHR user community composed of safety net health centers. The Alliance is an innovator and national leader in using health information technology (HIT) among FQHCs. The Alliance links 67 community health center practices in the metropolitan Chicago area; all are Public Health Service 330-funded FQHCs with federal mandates to care for medically underserved areas. Patients are mostly African American, Latino and low income. Alliance FQHC's share a common EHR (GE Centricity®). Drs. [name] and [name] have a long history collaborating with the Alliance and [name]. We will work specifically with Near North Health Services Corporation, randomizing seven of their clinics.

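### The Aim 3 tests of H4-H7 ignore clustering by clinic; for H4 a nominal 5% test would run at an illustrative 6-7%, and higher if counseling clusters more than the knowledge score

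*Combined protocol and SAP*

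**What the plan says.** Section 11.1 (Aim 1) sets the design: "The proposed trial uses a cluster-randomized design where the practice location is the unit of randomization". It also says "We will randomize 12 locations to two arms (usual care, EMC2) resulting in 6 per arm", from matched pairs "with one location from each pair randomized to each arm". To allow for correlation within practice, the Aim 1 text states "we will use GLMMs for analyses of all data", with practice location as a random effect. Aim 2 takes this up: "We will repeat all GLMM analyses described in Aim 1".

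Aim 3 does not. For the between-arm hypotheses on fidelity it says "Bivariate analyses will be performed to compare relevant outcomes for H4-H7 between arms using t-tests, Wilcoxon Rank-Sum" or chi-square tests, as appropriate. It names no clinic effect, variance inflation or between-clinic degrees of freedom.

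The number of clinics is not settled. Section 11.1 and section 29 speak of 12 locations. Sections 3.1, 3.2 and 19.1 speak of seven ("randomizing seven of their clinics"), and section 3.2 lists three of them as intervention clinics, which leaves four controls.

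**The concern.** When clinics are randomized, the difference between arms carries between-clinic variation as well as patient variation. A t-test, rank-sum test or chi-square test on individual patients counts only the second part. The plan recognizes this elsewhere: it uses a random clinic effect for Aim 1 and a variance inflation factor in section 11.2. The same patients in the same clinics supply H4-H7.

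The general mixed-model sentence can be read in two ways. Read literally, it covers H4-H7 and contradicts the Aim 3 sentence. Read as part of Aim 1, which is how Aim 2 refers to it, it leaves Aim 3 with no adjustment. Either way the tests that Aim 3 names ignore the clinic, and an analyst cannot tell which test is pre-specified.

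Section 1.2 states H4-H7 as hypotheses against usual care, so these are more than descriptive tables. At stake is a false claim that the intervention changed counseling or another fidelity outcome. H4 concerns what clinic staff do, so clustering is plausible. Section 9.1 calls usual-care counseling variable, but does not say that it varies by clinic.

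**Working it through.** **Inputs from the documents.** 600 enrolled per arm (section 23). ICC 0.001, given for the knowledge score only (section 11.2). Either 12 locations of about 100, or three intervention and four control clinics. Prescriber or nurse counseling is a yes/no item asked at the baseline interview (section 9.4), so enrolled numbers are used.

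**Assumptions.** Two-sided 5% level (section 11.2 gives 5% for the knowledge score; none is stated for Aim 3). The knowledge ICC applies to counseling. Equal clinic sizes within arm, unless stated otherwise.

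**The plan's own figure.** There is none for H4-H7. The nearest is the detectable knowledge difference of 5.5 points (SD 28.4, 480 per arm). With a design effect (DEFF) of 1 + 79 × 0.001 = 1.079, (1.960 + 0.842) × 28.4 × √(2 × 1.079/480) = 5.34. The stated 5.5 is slightly conservative; this does not bear on Aim 3.

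**Error of the unadjusted test.** With clinic size m and coefficient of variation of size CV:

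DEFF = 1 + [m(1 + CV²) − 1] × ICC, averaged over arms; actual error = 2 × [1 − Φ(1.960/√DEFF)].

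- 12 × 100: DEFF = 1 + 99 × 0.001 = 1.099; error 6.15%.
- 3 × 200 v 4 × 150: DEFF = (1.199 + 1.149)/2 = 1.174; error 7.05%.

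A beta-binomial simulation of the chi-square test (200,000 runs per setting, event rates 0.3 and 0.5) gave 6.2-6.5% and 7.0-7.5%.

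**Unequal clinic sizes.** The plan says only "We will accrue ~100 patients per location, on average". At ICC 0.001:

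| Assumed CV | 12 locations: DEFF, error | Seven clinics: DEFF, error |
|---|---|---|
| 0.5 | 1.124, 6.45% | 1.218, 7.57% |
| 1.0 | 1.199, 7.35% | 1.349, 9.15% |

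**Larger ICC, equal sizes.** An error of 10% needs DEFF = (1.960/1.645)² = 1.42. That is an ICC of 0.42/99 = 0.0042 with 12 locations, or 0.42/174 = 0.0024 with seven clinics. At an assumed ICC of 0.01 the DEFF is 1.99 or 2.74, and the error 16.5% or 23.6%.

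**Pair matching (12 locations).** If matching removes half the between-clinic variance (assumed), DEFF falls by 100 × ICC × 0.5. At ICC 0.001 it is 1.049 (5.6%); at 0.01 it is 1.49 (10.8%).

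**Do the alternatives hold their level?** In simulation:

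- Clinic-level t-test: 4.2-5.2% over ICC 0.001 to 0.05, with equal sizes and with CV 0.5.
- Paired t-test on six pairs: 4.2-5.1%.
- Logit random-intercept model with between-clinic degrees of freedom: 2.1-2.3% (12 locations) and 1.0-1.1% (seven clinics) at ICC 0.001; 3.6-4.6% at 0.01; 4.6-4.9% at 0.05. Its clinic variance was estimated as zero in 47-49% of runs at ICC 0.001.
- The same model with a normal reference: 6.7-9.8% at ICC 0.01, so the degrees of freedom matter.

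**Power.** At an assumed 50% rate and 80% power, the unadjusted detectable difference is 2.802 × √(2 × 0.25/600) = 8.1 points. With √(0.25 × 2 × DEFF/600) as standard error and noncentral-t multipliers of 3.110 (10 df) and 3.514 (5 df):

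| Design | ICC 0.001 | ICC 0.01 (assumed) |
|---|---|---|
| 12 locations, 10 df | 9.4 | 12.7 |
| Six pairs, 5 df, pairing removes no variance | 10.6 | 14.3 |
| Seven clinics, 5 df | 11.0 | 16.8 |

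**The case against.** The best defense is that the plan already covers this. The Aim 1 text applies mixed models to all data and promises ICCs for all outcomes; if that includes fidelity outcomes, the bivariate tests are a first look and only a cross-reference is missing. But both sentences stand in the Aim 1 plan, and the later Aim 3 text is specific and names other tests. The ambiguity itself needs correcting.

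Second, the documented effect is small. At the plan's only ICC the error is 6-7%, the outcomes concern fidelity, and Aim 3 is said to inform the qualitative work of Aim 4. This stands, and it limits the weight of the point. The larger error rates rest on assumed ICCs and size variation.

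Third, the 600 per arm is an inference. Under the first contact method in section 3.1 the baseline interview is a later call than consent, so completers may be fewer. The effect is slight: 12 × 80 gives 5.9%.

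Fourth, not every hypothesis can be tested as measured. Section 9.4 defines clinic follow-up as contact after concerns reported to the IVR system, which usual-care patients do not use, so H7 has no control counterpart. It lists no fidelity item for H6. These are separate gaps; they do not remove the error for H4 and H5, which are asked in both arms.

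**Conclusion.** The concern holds. The tests named for Aim 3 do not match the randomization. For H4 the illustrative error of a nominal 5% test is 6.2% (12 locations) to 7.0% (seven clinics), given the borrowed ICC, equal clinic sizes within arm and 600 per arm. A larger ICC or unequal clinic sizes raise it; effective pair matching lowers it. No error rate is claimed for H5-H7 or for pharmacist counseling. The plan should be corrected, but the point is confined to fidelity outcomes and does not affect the primary analysis.

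**What to change.** Replace the Aim 3 sentence so that every between-arm test of H4-H7 that can be run respects the clinic.

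- **Preferred:** compare clinic-level proportions or means by t-test, with degrees of freedom from the clinics actually randomized: 5 for seven unpaired clinics, 10 for 12 unpaired locations, or a paired test with 5 if the six matched pairs are kept.
- **Alternative:** the mixed model already planned, with a random practice-location intercept and between-clinic degrees of freedom, and without the treatment-by-time term where an outcome is asked once. State in advance what is done if the clinic variance is estimated as zero.
- Keep the bivariate tests as description only, and say whether the general mixed-model sentence covers Aim 3.
- Reconcile the 12-location and seven-clinic texts, since they set the degrees of freedom.

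This takes one or two sentences in section 11.1, plus that reconciliation, with no new data or software. The price is larger p-values and the loss of power tabulated above. The mixed model loses further power at ICC 0.001, where it is conservative.

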1. OBJECTIVES

1.1 Specific Aims

Aim 1: Test the effectiveness of an EHR-based Medication Complete Communication (EMC2) strategy to improve patient understanding of medication risks, patients’ demonstrated safe use, and the detection of patients’ adverse drug events.

Aim 2: Assess whether the EMC2 Strategy can reduce disparities in understanding and demonstrated safe use by patient literacy level, English proficiency, and age compared to usual care.

Aim 3: Evaluate the effectiveness and fidelity of the EMC2 Strategy to promote provider counseling, deliver patient Rx information, monitor use, and inform providers of potential harms.

Aim 4: Explore patient, provider, and health system barriers to implementation and effectiveness.

Aim 5: Determine the cost of delivering the EMC2 strategy from a health system perspective.

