9.2 Description of the intervention

1. Provider Medication Alert: If a prescribing clinician attempts to place a new order or change an existing prescription for one of the study medications (Table 1), an EHR-generated alert will notify the provider that the medication requires patient counseling. This alert will contain a brief description of the top risks or side effects that patients may experience while taking this medication; this information is directly derived from the FDA-approved Medication Guide for the drug. The pop-up will also include an html link to the 1-page Med Sheet, which they can use to further inform their counseling.

2. Automated Delivery of Med Guide Summary: When the patient leaves an encounter and checks out, the medication order in Centricity will automatically cue printing of the 1-page Med Guide Summary.

STU#: 00201638

3. IVR Follow-Up Phone Assessment: One day after a patient's baseline interview (which will occur within 1-30 days post-visit), the patient will be prompted to call into the automated IVR system. The goal of the IVR call is to confirm patients' understanding and safe use of the prescribed high-risk medication they are taking, and to screen for any adverse drug events that may arise from having taken the medicine.

The call will investigate content areas that will be standard across all medications under study: 1) medication recognition, 2) medication fill (and fill barriers, if applicable), medication adherence (and adherence barriers, if applicable), perceived effectiveness, and side effects experienced. The IVR content was derived from the Med Guide Summaries. Patients are able to speak their responses as "yes", "no", or "do not know" or use their keypad.

To facilitate the call, patients will be sent (via text or phone call) a call-in number for the IVR system so that they are able to make the call at their convenience. The text with the call-in number will be sent on the day following the patient's baseline interview. (The day lag is needed so that the participant's medication data can first be uploaded to the IVR system in preparation for the call).

If subjects have not used the system after one day, a reminder text message, again including the call-in number, will be sent by the RA at Northwestern. If subjects have not used the system after two days, the RA at Northwestern will call the patient to remind them to call into the system and to ensure they have the call-in details.

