4. Clinician Lab Reports. When a patient is flagged as having a medication-related concern based on the responses they give to the IVR system, the system will send an HL7 message to Alliance, which will appear as a 'lab report' in the patient's chart and sent to a centralized desktop at the clinic. The lab report will indicate the specific nature of the medication concern (e.g. fill concern, adherence concern, or safety concern), allowing the clinic staff to respond appropriately. Each clinic will be able to detail a reasonable response based on the type of concern reported. The default plan is that this role will be undertaken by nurses involved with care management responsibilities.

5. Nurse Counseling: Depending on the nature of the concern flagged, the IVR lab report will trigger the expectation for a clinic nurse to respond. Each FQHC can tailor their proper protocol for responding. During the IVR call, patients are told that issues will be reported to their clinic but that if they have concerns, they should call the clinic directly. The IVR system provides their clinic phone number before ending the call. This is done so that a patient is not left waiting for a response from the clinic when the clinic doesn't feel that the lab report warranted follow-up.

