Aim 5 Analysis Plan: We will directly measure and assess the provider perspective costs of developing and running the EMC2 Strategy. Specifically, we will estimate the incremental cost of the intervention relative to usual care from the perspective of the Alliance and each FQHC implementing this process and tools. The primary costs of running the EMC2 Strategy involves the limited expenses around printing (printer ink, paper, staff time) as a result of generating new medication information with after-visit summaries. However, we will include estimates for minimal programming maintenance, for both GE Centricity EHR and the IVR system, and will test the sensitivity of results to changes in the maintenance requirements in terms of programmer hours. We also will separately track development costs for software and other programming requirements based on programmer hours. Staff/programmer costs will be measured using tracked time spent on the intervention and wage estimates. We will test the sensitivity of operational costs to different assumptions about the potential use of variable staff using different salaries but assuming the same proficiency in terms of time required. Further, we will assess the sensitivity of estimates to different proficiency levels that could arise from learning by doing.

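### Aim 5 costs EMC2 only to the Alliance and its health centers, so IVR prompting and operation by outside staff go uncounted and the running cost may be understated

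*Combined protocol and SAP*

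**What the plan says.** Section 1.1 states Aim 5 as: "Determine the cost of delivering the EMC2 strategy from a health system perspective". The Aim 5 paragraph of section 11.1 calls this the provider perspective and plans an incremental cost against usual care, "from the perspective of the Alliance and each FQHC implementing this process and tools".

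On running costs, the same paragraph says: "The primary costs of running the EMC2 Strategy involves the limited expenses around printing (printer ink, paper, staff time". It then widens the list: "we will include estimates for minimal programming maintenance, for both GE Centricity EHR and the IVR system". It also has a general labour clause: "Staff/programmer costs will be measured using tracked time spent on the intervention and wage estimates". Development costs are tracked separately. Sensitivity analyses cover maintenance hours, staff proficiency, and "different assumptions about the potential use of variable staff using different salaries but assuming the same proficiency in terms of time required".

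Section 9.1 lists five EMC2 activities: provider counseling, delivery of the Med Guide Summary, the IVR assessment, the IVR lab report and nurse counseling. Section 9.2 says how patients are brought to the IVR. After one day without use, "a reminder text message, again including the call-in number, will be sent by the RA at Northwestern"; after two days, the same research assistant telephones. Section 6 gives facilitation of the IVR to Boston Medical Center. On nurses, section 9.2 says that "the IVR lab report will trigger the expectation for a clinic nurse to respond".

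**The concern.** A patient has to call in to the IVR. The lab report and the nurse response can follow only if the patient does so. The reminders are therefore part of how three of the five activities reach patients, and they are made by staff of an institution that is neither the Alliance nor an FQHC. The same holds for the institution that runs the IVR.

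A costing confined to the Alliance and the FQHCs has no place for labour that others pay for. A health system adopting EMC2 would have to supply that labour, buy it or replace it. Section 2.3 presents the strategy as one whose cost is not prohibitive to clinics, so a running cost that leaves out part of delivery bears directly on what Aim 5 is meant to show.

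**Working it through.** The plan states no cost figure, so there is nothing to reproduce. The check sets each delivery task against the Aim 5 paragraph.

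| Task | Who does it | Inside the Alliance/FQHC perspective? | In the Aim 5 paragraph? |
|---|---|---|---|
| Provider counseling | Clinic prescribers (9.2) | Yes | Not named; tracked-time clause can cover it |
| Printing the summary | Clinic (9.2) | Yes | Named as primary |
| First call-in message | Sender not stated (9.2) | Unclear | Not named |
| Reminder text and call | University research assistant (9.2) | No | Not named |
| IVR operation | Another medical center (6); daily data upload by the university (11.3) | No | Programming maintenance only |
| Nurse response | Clinic nurses by default (9.2) | Yes | Not named; tracked-time clause can cover it |

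Two tasks fall outside: the reminders, and IVR operation beyond maintenance. None of the planned sensitivity analyses brings them back, since these vary hours, salaries and proficiency for work already counted. An omitted cost line can only lower the total, so the direction is settled.

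The size is not. The documents give no wages, minutes per task, IVR completion rate or share of calls flagged. The following illustration uses 600 intervention patients (section 23); **every other input is assumed**.

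- Printing, paper and ink plus staff time per patient. Low: $0.05 × 600 = $30. High: ($0.20 + 1/60 h × $20) × 600 = $320.
- Research-assistant prompting, as average minutes per enrolled patient. Low: 2/60 h × $18 × 600 = $360. High: 20/60 h × $28 × 600 = $5,600.
- Nurse response. Low: 600 × 0.3 calling in × 0.2 flagged = 36 reports; 36 × 5/60 h × $30 = $90. High: 600 × 0.8 × 0.5 = 240 reports; 240 × 30/60 h × $45 = $5,400.

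Per enrolled patient, prompting is $0.60 to $9.33 and printing $0.05 to $0.53.

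Two cautions apply. First, summaries also print for patients who never enroll (sections 3.1 and 9.1), so the printing total is too low. At the high unit cost of $0.533, 675 summaries already cost $360. Seventy-five unenrolled patients would therefore close the gap between the highest printing and the lowest prompting figure. Second, patients who are not taking the drug and do not plan to take it do not go on to the IVR (section 9.3), so 600 is an upper limit for prompting and nurse response. The illustration shows that prompting could matter; it does not rank the items.

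**The case against.** The strongest reply is that the plan is broader than its sentence on printing. It counts IVR maintenance although another institution facilitates the IVR, so it does not set everything supplied from outside to zero. It measures staff cost by tracked time without limiting roles. A provider perspective is a legitimate choice, and the Alliance together with its FQHCs might fairly be called the health system. Some prompting may also be a trial activity that routine use would automate or drop. All of this stands. It supports keeping the planned estimate and saying that the cost may, rather than will, be understated. It does not bring the reminders in, because time paid for by the university is not a cost to the Alliance or an FQHC, however it is tracked. Doubt over whether prompting is research or delivery is a reason to show the result both ways.

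A reader might also infer that nurse time is excluded. The documents do not support that. Nurses work in the clinics and so lie inside the perspective, and the tracked-time clause can cover them. Section 9.4 lists no staff time log, but it lists no source for printing or programmer hours either, and those are clearly to be measured. Its silence is weak evidence. What remains is that nurse time is not named.

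A reader might further conclude that printing is a trivial share of the true running cost. That rests wholly on assumed inputs, and printing includes staff time and unenrolled patients.

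**Conclusion.** The point holds in a limited form. Under the perspective stated in section 11.1, the IVR reminders made by university staff, and IVR operation beyond programming maintenance, are not counted. The running cost may therefore be understated against the health-system perspective of section 1.1. The conclusion on direction assumes that an adopting system would need some of this work; the documents do not allow its size to be set.

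It would go too far to say that cost and effect will describe different interventions. Section 11.1 plans no cost-effectiveness ratio, and some of the prompting might not be needed in routine use. The matter touches a descriptive aim and no primary endpoint. It is a cheap improvement.

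**What to change.** In the Aim 5 paragraph of section 11.1:

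1. Keep the estimate from the Alliance and FQHC perspective as planned.
2. Add a sensitivity analysis that values the IVR prompting and IVR operation done by outside staff as if the adopting health system supplied them. Report the running cost with and without these lines.
3. Name nurse response to IVR reports among the tracked staff costs.
4. State the sources of the counts. Flagged calls can come from the IVR responses, which section 10.1 keeps until the analyses are complete; the HL7 messages are deleted after 7 days and are not a lasting source. Reminder texts and calls can be recorded in the study tracking database of section 11.3. That section mentions an interview call log but not IVR reminders, so one added field may be needed. State also who sends the first call-in message.

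The cost is a little extra logging and analysis, and the version with the added lines will show a higher cost.
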